#### 5.8. **General Concomitant Medication and Supportive Care Guidelines**

In general, subjects may receive full concomitant and supportive care throughout this trial with the following considerations:

- Subjects may not receive any other approved or investigational anti-neoplastic therapies for the treatment of prostate cancer from time of consent through prostatectomy.

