## 12.2. Reference standard definition:

12.2.1. Histopathology/Biopsy will be the primary determinate of tissue positivity and negativity for prostate cancer disease. Pathology date, organ, and location as well as any notes related to the pathology will be obtained from the subject chart. The anatomical region/sub-region the pathology occurred in will be assigned by the investigator team:

Ga-PSMA-HBED-CC positive findings are aimed to be confirmed by histopathology/biopsy if clinically feasible. Pathology performed 60 days before or after the Ga-PSMA-HBED-CC PET will be available for correlation.

Histopathological procedures and biopsies will be performed as clinically indicated and as per institutional protocol.

12.2.1.1. Lymph Nodes, Visceral Lesions, and Bone Lesions positive for disease by pathology.

- Lesions with positive pathologic confirmation will be regarded as positive for disease. The regionality of the resected tissue will be assigned into respective regions and sub-regions as described above in Table 12.2.

12.2.1.2. Lymph Nodes and Visceral Lesions negative for disease by pathology.

- Tissue removed and negative for pathology are considered negative for prostate cancer disease, unless subsequent conventional imaging or Ga-PSMA-HBED-CC PET imaging demonstrates that targeted tissue were not resected. In this case:

- i. Subjects can be rescanned with dedicated CT, MRI, or Ga-PSMA-HBED-CC PET/CT to determine if the suspicious Ga-PSMA-HBED-CC tissue was removed. If the tissue is confirmed as removed, this is considered negative for disease.

ii. If  $^{68}\text{Ga}$ -PSMA-HBED-CC PET/CT positive tissue is still present, a needle biopsy can be pursued at the discretion of the treating physician. Images of the procedure will be reviewed to determine if the correct tissue was biopsied.

- If the  $^{68}\text{Ga}$ -PSMA-HBED-CC PET/CT positive tissue was biopsied, a negative pathologic finding of the biopsied tissue is considered negative for disease.
- If the  $^{68}\text{Ga}$ -PSMA-HBED-CC PET/CT positive tissue was biopsied, a positive pathologic finding of the biopsied tissue is considered positive for disease.
- If biopsy or re-biopsy is not performed, or the wrong tissue was biopsied, change in node size as measured by conventional imaging and as defined below will be the criteria by which disease status will be defined.

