12.2.1.3. Bone lesions: Given the high rate of false negative biopsies for osseous metastases in subjects with prostate cancer, subjects with negative bone biopsies of  $^{68}\text{Ga}$ -PSMA-HBED-CC PET positive lesions will be further evaluated:

- If pathology demonstrates an alternative diagnoses that is known to be  $^{68}\text{Ga}$ -PSMA-HBED-CC positive (eg Renal Cell Carcinoma metastases, Paget's disease), then this will be considered negative for disease.
- If pathology is indeterminate, then follow-up imaging as described below will be performed as per clinical standards at the site.

12.2.1.4. Although not routinely performed during standard practice, immunohistochemical staining for PSMA of tumor specimens (primary and lymph node metastases) may be performed, although not required.

12.2.1.5. All regions not sampled for biopsy/histopathology will be designated as indeterminate for disease by pathology. Conventional imaging follow-up may be used in these cases to determine tissue status.

12.2.2. Follow-up Imaging will be used as a secondary assessment for prostate cancer in the event pathology information is not available:

All subjects will be tracked for follow-up conventional imaging between 3-12 months post  $^{68}\text{Ga}$ -PSMA-HBED-CC (dedicated CT, MRI and/or bone scan) as per site standard of care. If no follow-up imaging has been performed within the 9 months following the  $^{68}\text{Ga}$ -PSMA-HBED-CC scan, then the research study will pay for an additional follow-up CT scan to be performed in the 9-12

month window post-Ga-PSMA-HBED-CC scan. Follow up imaging will only be performed on subjects that have positive Ga-PSMA-HBED-CC findings because conventional imaging assessment for disease is primarily targeting suspicious lesions identified by Ga-PSMA-HBED-CC PET/CT. Interpretation of follow-up imaging will be performed by local read. Preferably, the follow-up conventional imaging should be the same modality/modalities as the initial staging work-up to allow for reproducible and accurate comparisons. Conventional imaging standards as described below will be used to determine tissue positive for prostate cancer disease. Conventional imaging will not be used to determine negative prostate cancer disease regions due to its inherently low negative predictive value.

Tissue positive for prostate cancer disease based on follow-up imaging:

12.2.2.1. Lymph nodes will be assessed by change in size.

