#### 13.2.1. True positive patient:

13.2.1.1. **Ga PSMA-HBED-CC PET/CT positive for a regional node by internal blind reader:** pathology at prostatectomy is positive for a regional node that correlates in location to the PET images (location on pathology is determined by the urologist at the time of the surgery). Only one node needs to correspond between imaging and pathology for a patient to be considered a true positive.

13.2.1.2. **Ga PSMA-HBED-CC PET/CT positive for regional nodes by internal blind reader,** pathology negative for regional nodes, imaging after prostatectomy demonstrates the same node was not removed at surgery, and follow-up biopsy or imaging demonstrates presence of nodal disease as defined in Section 12.2.1.2 .

13.2.1.3. **Conventional imaging criteria for positive node on follow-up imaging:** imaging within 3-12 months, the node decreases by more than 30% (for patients undergoing systemic treatment or focal therapy at this site) or increase by more than 20% in short axis diameter in the absence of treatment (with a minimum of 3 mm in change in size) as defined in Section 12.2.2.1 .

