#### 13.2.3. False positive patient:

13.2.3.1. **Ga PSMA-HBED-CC PET/CT positive for regional nodes**

**by internal blind reader**, pathology at prostatectomy is negative, and imaging after prostatectomy demonstrates that node is no longer present as defined in Section 12.2.1.2.

13.2.3.2.  **$^{68}\text{Ga}$  PSMA-HBED-CC PET/CT positive for regional node by internal blind reader**, but pathology at prostatectomy is positive for node but in a different nodal region than the node seen on PSMA PET.

13.2.4. False negative patient:

13.2.4.1.  **$^{68}\text{Ga}$  PSMA-HBED-CC PET/CT negative for regional nodes by internal blind reader**, but pathology at prostatectomy is positive for regional nodes.

13.2.5. Non-evaluable patient:

13.2.5.1. Any subject that does not have sufficient data to meet the criteria for definition of true positive patient, true negative patient, false positive patient, or false negative will be classified as non-evaluable.

13.2.5.2. Patients with extrapelvic nodal metastases will not be included in this analysis for the primary endpoint if patients do not undergo prostatectomy.

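### A PET-positive, pathology-negative man whose first post-operative scan follows cancer treatment and shows no node can be scored as a false positive or a true positive

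*Combined protocol and SAP*

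**What the plan says.** **True positive.** Section 13.2.1.2 covers men with negative nodal pathology. It requires that "imaging after prostatectomy demonstrates the same node was not removed at surgery", and then biopsy or imaging evidence of disease. Section 13.2.1.3, numbered as a separate item, gives the size criterion: "imaging within 3-12 months, the node decreases by more than 30% (for patients undergoing systemic treatment or focal therapy at this site", or growth of more than 20% without treatment. It refers to 12.2.2.1 and mentions neither pathology nor whether the node was left in place.

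**False positive.** Section 13.2.3.1 applies when "pathology at prostatectomy is negative, and imaging after prostatectomy demonstrates that node is no longer present", with reference to 12.2.1.2.

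**Reference standard.** Section 12.2.1.2 sets the default: "Tissue removed and negative for pathology are considered negative for prostate cancer disease, unless subsequent conventional imaging" or PSMA PET shows that the target was missed. After a rescan, "If the tissue is confirmed as removed, this is considered negative for disease". Size change decides only if PET-positive tissue persists and was not validly biopsied. Section 12.2.2 makes follow-up imaging secondary to pathology. For systemic treatment, 12.2.2.1(a) adds a PSA fall of more than 50%.

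**Timing.** The rescan that checks removal is optional and has no date (5.7.1, 12.2.1.2(i)). Follow-up imaging is tracked over 3 to 12 months. If none has been done by nine months, "then the research study will pay for an additional follow-up CT scan to be performed in the 9-12" month window (12.2.2). Section 5.8 states: "Subjects may not receive any other approved or investigational anti-neoplastic therapies for the treatment of prostate cancer from time of consent through prostatectomy". It sets no limit after surgery. Lesions are measured on the baseline and the follow-up CT or MRI (5.7.5).

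**The concern.** A node can be missing from a post-operative scan because the surgeon removed it or because treatment made it disappear. If treatment began before the first post-operative scan, that scan cannot tell the two apart. Because size is measured against a pre-operative baseline, the apparent shrinkage spans the operation.

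The error can go either way. A benign node that was resected could count as a treatment response that proves disease. A metastasis that was missed at surgery and then responded could count as removed, and so as a PET error.

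Men who are PET positive and pathology negative determine PPV and specificity, both part of the primary endpoint. Section 13.1 already names the reference standard as a source of uncertainty, and plans to use the results to set the target sensitivity of a larger study.

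**Working it through.** **Step 1: trace the cases.** All three men are PET positive with negative nodal pathology.

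1. *A scan after surgery still shows the node, which then shrinks on treatment.* Removal is not confirmed, so 13.2.3.1 fails. Without a valid biopsy, 12.2.1.2(ii) leads to the size rule. Result: true positive, subject also to the PSA fall if treatment was systemic. The documents settle this case.
2. *A scan before any post-operative treatment shows the node gone.* Removal is confirmed under 12.2.1.2(i), and the size rule is not reached. Result: false positive. The documents settle this case too.
3. *The first post-operative scan comes after systemic or focal treatment and shows no node.* Section 13.2.3.1 is met, because pathology is negative and the node is absent. Section 13.2.1.3 is met on its face, because disappearance is a 100% decrease and 100% > 30%. This assumes the node was visible on the baseline CT or MRI and measured at least 3 mm, so that the minimum change is also met. Section 13 does not say which rule prevails.

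**Step 2: does the PSA condition separate case 3?** Not reliably. It applies only to systemic treatment; the 30% shrinkage route for targeted treatment alone in 12.2.2.1(b) has no PSA condition. Section 12.2.2.1(a) also states no reference PSA. The baseline value in 6.1.5 is pre-operative, so prostatectomy alone might produce the fall. That last step is an inference, not something the documents say.

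**Step 3: effect of one man.** The plan gives no figure for this subgroup. Its half-width table in 13.1 is reproduced by 1.96 × √(p(1−p)/30); for p = 0.80 this gives 14.3%, as printed. The point does not depend on that table.

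For scale, take the prospective 30-man study in Section 2.3, reported with sensitivity 64%, specificity 95%, PPV 88% and NPV 82%. The only whole-number table of 30 men that rounds to all four is TP 7, FN 4, FP 1, TN 18.

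| Measure | Formula | Man scored FP (7, 4, 1, 18) | Man scored TP (8, 4, 0, 18) |
|---|---|---|---|
| Sensitivity | TP/(TP+FN) | 7/11 = 63.6% | 8/12 = 66.7% |
| Specificity | TN/(TN+FP) | 18/19 = 94.7% | 18/18 = 100% |
| PPV | TP/(TP+FP) | 7/8 = 87.5% | 8/8 = 100% |
| NPV | TN/(TN+FN) | 18/22 = 81.8% | 18/22 = 81.8% |

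I used the usual definition of sensitivity. The formula printed in 13.1 has false positives in the denominator, which is PPV; on that formula the change would be from 87.5% to 100%.

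**The case against.** The strongest objection is that the two Section 13 lines should not be read without the Section 12 rules they cite. Section 12.2.1.2 asks for confirmed removal, admits size change only when tissue persists, and ranks pathology first. A reader might infer from Section 13 alone that the plan never separates surgical removal from treatment response. The documents do not support that: Section 12 settles cases 1 and 2. This part of the objection stands and confines the point to case 3.

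Section 12 does not settle case 3 cleanly. It leans towards false positive, because nothing shows that the target was missed. But it does not define what confirms removal, and absence after treatment looks the same either way. Whether pathology is available for that particular node depends on whether the node was removed, which is the open question.

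It can also be said that 13.2.1.3 is only the imaging criterion for 13.2.1.2, since it mentions neither PET nor pathology. That is a sensible reading and probably the intended one. The text does not say so: the item has its own number under the true-positive heading, and it points to 12.2.2.1 rather than to 12.2.1.2, where the requirement that tissue persists is found.

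The research CT at 9 to 12 months is weak support for the timing argument, because 6.4.2 ties a research CT to lesions outside the pelvis. The argument does not need it, since routine imaging at 3 to 12 months can also follow treatment.

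Finally, the non-evaluable category in 13.2.5.1 is for men who meet none of the definitions. It does not address a man who meets two.

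**Conclusion.** The point holds for one pattern only: PET positive, pathology negative, treated before the first post-operative scan, and node absent on that scan. For such a man two primary-endpoint rules conflict, and the plan does not say which governs.

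The number of men is not given and may be none. A reader might assume two or more in 30, but the documents do not support that. The 30-man study in Section 2.3 is consistent with one false positive in all. The 130-man retrospective study there (sensitivity 65.9%, specificity 98.9%, accuracy 88.5%) also fits one: TP 27, FN 14, FP 1, TN 88. Only some false positives would show this pattern.

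Per man affected, and assuming the 7/4/1/18 table, PPV changes by 12.5 points, specificity by 5.3 and sensitivity by 3.0; NPV does not change. The study is a descriptive pilot with no significance testing, so no formal inference is at risk. The correction is still worth making before the data are read, because it concerns stated primary-endpoint rules and is cheap.

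**What to change.** The change is to classification only. It asks for no additional scan and does not touch treatment.

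1. **Section 13.2.1.3.** State that, for operated men, it applies only where post-operative imaging still shows the node, or where its region was not sampled by pathology (12.2.1.5), and subject to every condition in 12.2.2.1. In a dissected region, disappearance between the pre-operative and the first post-operative scan is not a decrease. A node still visible after surgery may be compared with its baseline size, since it was plainly not removed; requiring a second post-operative scan would discard valid cases.
2. **Sections 12.2.1.2(i) and 13.2.3.1.** Treat absence as confirmed removal only if the scan precedes any post-operative anti-neoplastic treatment. If absence in a dissected region is first seen after treatment, keep the 12.2.1.2 pathology default (false positive) and flag the man as removal not shown.
3. **Reporting.** Give one bounding table that counts the flagged men as true positives.

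The cost is the wording in Sections 12.2 and 13.2, plus recording treatment start dates and scan dates from the chart already under review. Slightly fewer men can be upgraded to true positive, so sensitivity and PPV may look a little less favourable. The default still scores a metastasis that responded as a PET error; the bounding table shows how much that could matter.

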i. Positive for disease:

- a. -For subjects undergoing systemic treatment (alone or in combination with targeted treatment): If on post-treatment follow-up imaging within 3-12 months, visually suspicious lymph nodes seen on CT or MRI decrease by more than 30% in short axis diameter and PSA declines by more than 50%.
  - If PSA increases by more than 25% (PCWG3 definition of recurrence) on systemic therapy, then an increase in the size of lesion by more than 20% in the short axis diameter will be considered a positive for disease.
- b. In subjects with localized suspected lymph node(s) receiving targeted treatment without concomitant systemic treatment there are two ways to achieve positive for disease designation:
  - If the subject shows a decrease of PSA by greater than 50% after targeted treatment and the lymph node does not enlarge (change in size less than 20% in the short axis diameter or less than 3 mm increase in short axis diameter) [OR]
  - If on post-treatment follow-up imaging within 3-12 months, lymph nodes seen on CT or MRI decrease by more than 30% in short axis diameter (with a minimum of 3 mm in change in size)
- c. For untreated subjects: If on follow-up imaging within 3-12 months, lymph nodes seen on CT or MRI increase by more than 20% in short axis diameter (with a minimum of 3 mm in change in size).

ii. Negative for disease:

- Conventional Imaging follow-up will not be used for assessment of negativity for disease.

iii. Indeterminate for disease

- Regions with no lymph nodes determined to be positive by the conventional imaging criteria described above and without pathology will be designated regions indeterminate for prostate cancer disease.
- Subjects that have had neither pathology sampling, nor conventional imaging follow up will have all regions designated as indeterminate for disease by reference standard.

12.2.2.2. Visceral lesions (non-lymph node soft tissue or organ) and prostate bed and prostate lesions will be assessed by change in size.

i. Positive for disease:

- a. For subjects undergoing systemic treatment (alone or in combination with targeted treatment): If on post-treatment follow-up imaging within 3-12 months, visually conspicuous lesions seen on CT or MRI decrease by more than 30% in long axis diameter and PSA declines by more than 50%.

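### The follow-up imaging rule for a positive node in the primary endpoint (13.2.1.3) does not match the section it cites (12.2.2.1), so some nodes are positive under one and not under the other

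*Combined protocol and SAP*

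**What the plan says.** Section 13.2.1.3 gives the conventional imaging criteria for a positive node at 3 to 12 months. The shrinkage limb applies if "the node decreases by more than 30% (for patients undergoing systemic treatment or focal therapy at this site"). The growth limb is an increase above 20% in short axis "in the absence of treatment (with a minimum of 3 mm in change in size) as defined in Section 12.2.2.1". PSA is not mentioned.

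Section 12.2.2.1 sets the lymph-node criteria by treatment group:

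- Systemic treatment (item a): suspicious nodes must "decrease by more than 30% in short axis diameter and PSA declines by more than 50" per cent, with no millimetre minimum. There is a second route: "If PSA increases by more than 25% (PCWG3 definition of recurrence) on systemic therapy, then an increase in the size of lesion" above 20% in short axis also counts as positive.
- Targeted treatment without systemic treatment (item b): "If the subject shows a decrease of PSA by greater than 50% after targeted treatment and the lymph node does not enlarge", or nodes "decrease by more than 30% in short axis diameter (with a minimum of 3 mm in change in size").
- Untreated (item c): nodes "increase by more than 20% in short axis diameter (with a minimum of 3 mm in change in size").

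On nodes that miss these criteria, the same section says: "Conventional Imaging follow-up will not be used for assessment of negativity for disease". Without pathology, such a region is indeterminate. Under 13.2.5.1 a patient who fits none of the four categories is non-evaluable.

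**The concern.** 13.2.1.3 does more than point to 12.2.2.1. It restates a rule with different conditions and then says that the rule is the one defined there. An analyst who applies 13.2.1.3 as written and one who follows the citation can classify the same node differently, and no rule of precedence is stated.

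The point matters because this is a true-positive item of the primary endpoint. Section 13.1 names the reference standard as a particular source of uncertainty. It also plans to combine the results with those of sites that use the same reference standard definitions, in order to power a larger study. That use needs one fixed definition, settled before results are seen.

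**Working it through.** **Side by side.** I take focal therapy at the site (13.2.1.3) to mean the same as targeted treatment (12.2.2.1).

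| Situation | 13.2.1.3 | 12.2.2.1 |
|---|---|---|
| Systemic, shrinkage | >30%; no PSA condition; 3 mm unclear | >30% and PSA fall >50%; no 3 mm |
| Systemic, growth | no route | >20% with PSA rise >25% |
| Targeted, PSA route | no route | PSA fall >50%, node not enlarging |
| Targeted, shrinkage | >30%; 3 mm unclear | >30% and at least 3 mm |
| Untreated, growth | >20% and at least 3 mm | >20% and at least 3 mm |

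**The 3 mm bracket.** It follows the growth limb in 13.2.1.3.

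- Reading G (growth only): the 3 mm that 12.2.2.1(b) requires for targeted shrinkage is lost.
- Reading B (both limbs): 3 mm is added to systemic shrinkage, where 12.2.2.1(a) has none.

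Neither reading reproduces 12.2.2.1. For shrinkage the minimum matters only below a baseline of 3/0.30 = 10 mm, because above that a 30% decrease already exceeds 3 mm.

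**Test nodes** (hypothetical values).

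| Treatment | Short axis | PSA | 12.2.2.1 | 13.2.1.3 (G) | 13.2.1.3 (B) |
|---|---|---|---|---|---|
| Systemic | 10 to 6.5 mm (3.5/10 = 35% decrease) | -30% | not positive | positive | positive |
| Systemic | 10 to 13.5 mm (35% increase) | +30% | positive | not positive | not positive |
| Targeted | 8 mm, unchanged | -60% | positive | not positive | not positive |
| Systemic | 6 to 4 mm (2/6 = 33% decrease) | -60% | positive | positive | not positive |
| Targeted | 6 to 4 mm (33% decrease) | -20% | not positive | positive | not positive |
| Untreated | 10 to 13.5 mm (35% increase) | any | positive | positive | positive |
| Untreated | 6 to 8 mm (33% increase) | any | not positive | not positive | not positive |

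The first three rows conflict on either reading of the bracket. The next two depend on the reading.

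**Where the patient goes.** Take a PET-positive node left in place, with negative pathology. If it misses the imaging criteria it is not negative, because imaging cannot establish negativity. False positive under 13.2.3.1 requires the node to be gone. False positive under 13.2.3.2 requires positive pathology in a different region. Neither applies, so the patient is non-evaluable under 13.2.5.1.

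**Size per patient.** The plan does not say how many patients depend on this rule, so the inputs are assumptions drawn from the two pre-prostatectomy studies in Section 2.3.

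- Study of 130 patients: prevalence of nodal disease = (98.9 - 88.5)/(98.9 - 65.9) = 31.5%, from its specificity, accuracy and sensitivity. In 30 patients this is about 9.5.
- Study of 30 patients: its four rates fit 7 TP, 4 FN, 1 FP and 18 TN (7/11 = 64%, 18/19 = 95%, 7/8 = 88%, 18/22 = 82%), so 11 of 30 are node-positive.

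I therefore use 9 to 11 node-positive patients of 30, and sensitivity as TP/(TP+FN). The formula printed in 13.1 has false positives in the denominator, which is PPV. Moving one TP to non-evaluable removes the patient from numerator and denominator:

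- PPV: 7/8 = 87.5% becomes 6/7 = 85.7%, a shift of 1.8 points.
- Sensitivity, 10 positives: 6/10 to 5/9 (60.0% to 55.6%), 7/10 to 6/9 (70.0% to 66.7%), 8/10 to 7/9 (80.0% to 77.8%).
- Sensitivity, 9 positives: 6/9 to 5/8 (66.7% to 62.5%), 7/9 to 6/8 (77.8% to 75.0%).
- Sensitivity, 11 positives: 7/11 to 6/10 (63.6% to 60.0%), 9/11 to 8/10 (81.8% to 80.0%).

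The sensitivity shifts run from 1.8 to 4.4 points.

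**The plan's own figures.** The half-widths in 13.1 follow from 1.96 x sqrt(p(1-p)/30): 16.4, 15.5, 14.3, 12.8 and 10.7 points for 70% to 90%. All five match, and none depends on this rule.

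**The case against.** The best defence is that the document already shows which section governs. The opening of Section 12 says that the reference standard criteria are in 12.2 and names serial PSA measurements as part of them, and 13.2.1.3 closes by deferring to 12.2.2.1. On that view 13.2.1.3 is a loose summary. This is the more natural reading, but it is not stated. 13.2.1.3 also stands as its own item with its own thresholds, so someone who follows it literally gets different answers.

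A second defence is that the retained-node situation is already covered by 13.2.1.2. That item cites 12.2.1.2, which sends an unbiopsied node on to the size criteria that follow. A patient can therefore reach 12.2.2.1 without 13.2.1.3, and the two missing routes are not clearly lost. This stands, and it narrows the exposure mainly to nodes that pass the looser 13.2.1.3 and fail 12.2.2.1. The 10 to 6.5 mm node is one.

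Two stronger readings are tempting, and the documents do not support them:

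- A reader might infer a switch between true and false positive, so that one patient in eight PET-positives moves PPV by 1/8 = 12.5 points. For a retained node with negative pathology, the false-positive definitions and the bar on imaging negativity rule this out.
- A reader might infer that 13.2.1.3 plainly imposes 3 mm on systemic shrinkage. An 8 to 5.5 mm node (31%, 2.5 mm) with a 90% PSA fall would then fail it, and a 4.7 mm node, the mean true-positive size in the 30-patient study, would need a 3/4.7 = 64% change. Both hold only if the bracket covers shrinkage.

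Nor is the missing millimetre minimum under systemic treatment evidently a slip in 12.2.2.1. Section 12.2.2.2 follows the same pattern for visceral lesions.

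**Conclusion.** The mismatch is real and is in the current text. 13.2.1.3 omits the PSA condition for systemic treatment, omits two positive routes, and has a 3 mm bracket that fits 12.2.2.1 on neither reading. At least one kind of node, shrinking by more than 30% on systemic therapy (and by at least 3 mm) with a PSA fall of 50% or less, is positive under 13.2.1.3 and not under 12.2.2.1 however the bracket is read.

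The effect is small. A patient moves between true positive and non-evaluable, worth about 2 points of PPV and about 2 to 4 points of sensitivity each, assuming a starting PPV of 7/8 and 9 to 11 node-positive patients of 30. Histopathology decides most patients, so few are likely to be affected, though the plan gives no count. The analysis is descriptive, and no planned sample-size or precision figure changes.

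**What to change.** Reconcile the two sections so that one rule governs. The simplest way is to delete the restated thresholds in 13.2.1.3 and say only that the node meets the lymph-node criteria of Section 12.2.2.1, which Section 12 already treats as the home of the criteria. If the sponsor intends the conditions in 13.2.1.3 instead, 12.2.2.1 has to be changed to match, because 13.2.1.2 also leads there. This review takes no position on which PSA or millimetre threshold is right.

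The cost is a wording change, with no new data, visits or patients. It should be made before results are seen.
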